Erythropoietin Injections (Credentialled procedure): A dose (50 IU/kg body mass) of recombinant human EPO (PROCRIT, EPOETIN ALFA, Janssen Products, LP, Titusville, NJ, USA) will be injected subcutaneously 3 times per week for 4 week. Injections will be performed by credentialled study staff at USARIEM. The Office of Medical Support and Oversight (OMSO) will be the prescriber of prescription drugs used in this protocol, to include EPO. The dosing amount and frequency is on-label dosing equivalent to pediatric dosing. This dose and duration has previously been shown to be sufficient to result in hematological adaptions and increase physical performance (18, 19, 33). Hematocrit and hemoglobin will be checked weekly to ensure values remain $< 50\%$. If Hct increases above 50%, EPO injections will be stopped and Hct will be reassessed within 3 days. If hemoglobin increases more than 1 g/dL over a 1 week period EPO injections will be stopped and hemoglobin will be reassessed within 3 days. Reticulocyte count will also be assessed on the first injection day, then again during week 2 and 4 of the injection phase. Additionally, before starting prescribed exercise, volunteers will complete a short clinically relevant health questionnaire and have vital signs checked (blood pressure, heart rate, and SpO_2) which will take about 5 minutes by study staff. Copies of all health related information will be provided to the OMSO daily for review and tracking. After the final injection volunteers will continue to be

monitored for 2 weeks by participating in weekly blood draws and daily monitoring of vital signs and health questionnaire which will continue to be reviewed by OMSO. Study personnel conducting this procedure will be credentialed and listed on the DOA log with code "F."

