be infused for 100 min under resting fasted conditions to ensure isotopic steady-state is achieved prior to initiating exercise. Volunteers will then perform 90 min of steady-state ($\sim 55 \pm 5\%$ of $\dot{V}O_2$ peak) load carriage ($\sim 30\%$ body mass) exercise. During exercise $\dot{V}O_2$, $\dot{V}CO_2$, and HR will be measured 6 times at approximately 0, 20, 45, 60, 75, and 85 min. A total of 12 $\dot{V}O_2$, $\dot{V}CO_2$, and HR during the two carbohydrate tracer studies. Credentialled personnel performing venous catheterization will be listed on the DOA log with code "T."

Figure 4: Carbohydrate Tracer Study

[figure not shown]

Figure Legend:

 = Steady-State ($55 \pm 5\%$ $\dot{V}O_2$ peak) † = Muscle biopsy

* = Blood Sampling

Δ = $\dot{V}O_2$ / $\dot{V}CO_2$ and Heart Rate

Percutaneous Muscle Biopsy of the Vastus Lateralis (credentialled procedure): Percutaneous muscle biopsies will be obtained from the vastus lateralis using a 5 mm Bergstrom needle with manual suction while the volunteer is under local anesthesia (1% lidocaine or similar) according to the approved USARIEM SOP (40, 41). Muscle biopsies will be performed immediately before, after, and post load carriage exercise. Each volunteer will have a total of 6 muscle biopsies during the entire study. Credentialled personnel performing muscle biopsies will be listed on the DOA log with code "R."

Blood Sampling (credentialled procedure): Blood samples will occur after an overnight (10 hour) fast. Blood collection for safety blood draws and CO rebreathing will be conducted using venipuncture. Safety blood draws will occur once a week during the injection (4 times) and follow-up period (2 times) of the protocol. Blood will be collected using an indwelling catheter kept patent using IV saline at approximately -100, -20, 0, 20, 40, 60, 80, and 270 min during carbohydrate tracer studies or venipuncture for weekly monitoring of Hct by a USARIEM credentialled phlebotomist. Blood draws will occur once per CO rebreathing measure. Additionally a finger stick will be used to collect tract amounts of blood during these measures. A total of 26 venipuncture and IV blood draws (Appendix F) will be completed during this study taking ~ 360 mL of blood sampled from each volunteer over the protocol days (**Table 2**). Blood samples will be used for isotope analysis assessment of nutrient status, hormone responses, and inflammation (**Table 2**).

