Volunteers will be allowed to withdraw at any time without penalty or loss of benefits to which they would otherwise be entitled. They will do so by informing the PI, AI or a staff member of their intent to withdraw verbally or in writing (electronic or paper/pencil). They will then be asked to verbally discuss their choice to withdraw with the PI so that reasons for withdrawal can be documented. An investigator may stop an individual's participation in the study if the volunteer is unwilling or unable to complete study procedures. An investigator may also withdraw a volunteer if the individual becomes ill or injured or it would not be in the volunteer's best interest to continue. If the participant is withdrawn by the investigator or decides to

voluntarily withdraw him/herself, all further data collection will discontinue. Any samples or data collected prior to withdrawal will be maintained. Participants will be compensated for any blood draws they completed up until that point, and they will be asked to return any remaining food items that were provided, in addition to any wrappers and diet/activity logs that they had completed up to the point of withdrawal.

C4. PRIVACY FOR SUBJECTS

To protect the volunteer's privacy, all of their research-related records will be labeled or "coded" with an assigned research volunteer number that will not include their name or any other form of identifiable information. The principal investigator or project coordinator will keep the link between volunteer number and the volunteer's research records in a locked cabinet. Any documents that will require the volunteer's name, such as the consent form, will be kept in a locked cabinet separate from any research documents that contain the volunteer's ID number. The principal investigator and project coordinator are the only people who will be able to match the research volunteer number with any of their personal identifying information.

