Measures to Minimize Risks of Harm: To minimize side effects the study will use a low dose EPO injection equivalent to a pediatric dose. Before participants begin the prescribed exercise they will complete a short clinically relevant health questionnaire (**Appendix A**) and have their vital signs (blood pressure, heart rate, and SpO₂) assessed by study staff. Copies of all health related information will be provided to OMSO daily for review and tracking. Hemoglobin and Hct values will be measured weekly during EPO injections. To minimize risk of blood clots Hct values will be maintained < 50%. If Hct values increase > 50% EPO injections will be stopped. Volunteer will return to for another Hct check within 3 days. If hemoglobin increases more than 1 g/dL over a 1 week period EPO injections will be stopped and hemoglobin will be reassessed within 3 days. EPO injections will only be administered by credentialed staff at USARIEM. These individuals will follow administration procedures provided in the PROCRIT® prescriber information guide. Volunteers will continued to be monitored for 2 weeks after the injections are complete to ensure there are no complications from the EPO injections. The OMSO will be responsible for observing and monitoring adverse events of participants in this study.

Research Procedure Name: Exercise

Research Procedure Description: Exercise testing will occur on a cycle ergometer or treadmill. Exercise will be at various levels of intensity based on exercise protocol.

Research-related Risks: Exercise per se rarely provokes cardiovascular events in healthy individuals with normal cardiovascular systems. The prevalence of fatal events in the U.S. is approximately 1:133,000 to 1: 185,000 for men and 1:769,000 to 1:1,500,000 for women who are competitive high school and college athletes. For middle-aged and older adults the relative risk rises to 1:15,000 to 1:18,000 for individuals without a prior history of cardiovascular events. Current civilian and military guidelines state that individuals less than 40 years of age who have no symptoms of or known presence of heart disease or major coronary risk factors have a low risk for cardiac

complications during vigorous exercise. All volunteers in this study fall into this low risk category. Local muscle discomfort and fatigue may occur in active muscles during and shortly after exercise. Muscle soreness, ranging in intensity from mild to severe, may persist for 1 to 7 days.

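### C3 ends all data collection at withdrawal with no safety exception, while B5.3 and C6.1 promise two weeks of monitoring after EPO and do not limit it to completers

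*Protocol*

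**What the plan says.** C3 (Withdrawal from Research Participation) covers both ways out of the study. On the first, "An investigator may also withdraw a volunteer if the individual becomes ill or injured or it would not be in the volunteer's best interest" to go on. For that route and for a volunteer's own decision alike, the consequence is given in one clause: if the volunteer is withdrawn or should "voluntarily withdraw him/herself, all further data collection will discontinue". Material collected earlier is kept, and the volunteer is paid for the draws done so far. Safety follow-up is not mentioned.

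B5.3 (Erythropoietin Injections) says that after the final injection volunteers will be "monitored for 2 weeks by participating in weekly blood draws and daily monitoring of vital signs and health questionnaire", with the results going to the medical office (OMSO) for review. C6.1 (Exogenous EPO, measures to minimize risk) repeats the commitment and gives its purpose: "Volunteers will continued to be monitored for 2 weeks after the injections are complete to ensure there are no complications from the EPO injections". Neither section says what happens to this monitoring when a dosed volunteer leaves early.

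**The concern.** For a volunteer who has received EPO and is then withdrawn, C3 tells the site to stop collecting data, and B5.3 and C6.1 tell it to keep collecting for two weeks. The grounds for investigator withdrawal include illness, so the group affected includes people in whom a late drug effect would matter most. C6.1 names clots and raised blood pressure among the risks, with infarction and stroke as rare ones, and C6.3 states that volunteers gain no direct benefit.

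There is also a reporting consequence. If follow-up is complete for finishers and cut short for leavers, capture of adverse events depends on something that may itself be caused by an adverse event. With 8 completers planned, one unrecorded event could change the safety description of the study.

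**Working it through.** No power or alpha calculation applies. The check has three parts: whether the post-dose monitoring belongs to the study's own data collection, how much is lost, and who is affected.

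**1. Are the follow-up draws study draws?** B5.3 (Blood Sampling) gives the total: "A total of 26 venipuncture and IV blood draws". The inputs are:
- Tracer studies: 8 sampling times (B5.3), 2 studies: 8 × 2 = 16.
- CO rebreathing: one draw per measure, two measures before and two after the injection phase (Study Design Overview): 1 × 4 = 4.
- Safety draws: "Safety blood draws will occur once a week during the injection (4 times) and follow-up period (2 times) of the protocol": 4 + 2 = 6.

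Sum: 16 + 4 + 4 + 2 = 26, which reproduces the stated total. Without the two follow-up draws the count would be 24. Payment agrees: 26 × $50 = $1300, the figure in C2. The follow-up draws are therefore planned and paid as study draws.

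**2. Are the questionnaires study data?** B5.5 and C5 both list questionnaires among the instruments on which study data are recorded under the subject number. C3 pays a withdrawn volunteer only for draws already done, so it foresees none afterwards.

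**3. How much is lost per person?** The planned post-dose monitoring is 2 draws and, if daily means every calendar day, 2 × 7 = 14 checks.
- Withdrawn during the injection phase after at least one dose: 0 of 2 draws and 0 of 14 checks are done under C3.
- Withdrawn after the first follow-up week: 2 − 1 = 1 draw and 14 − 7 = 7 checks are lost.
- Withdrawn before any injection: nothing is lost, because no post-dose monitoring was due.

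**4. Who is affected?** Only volunteers dosed before leaving. The documents give no number or expected rate for them, so no study-wide total can be calculated.

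**The case against.** The best case against is that C3 concerns withdrawal from research, and that data collection there may mean research data only. The protocol has its own Data Collection section (B5.4). Its table lists body measures, diet, activity, substrate oxidation, performance and metabolic response, but not safety hematocrit, vital signs or the health questionnaire. OMSO is responsible for monitoring adverse events (C6.1), the adverse-event definition in C8.1 rests on timing relative to participation, and nothing in C8 ends reporting at withdrawal. A site could stop research testing under C3 and carry on with safety checks.

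This reading is possible, and it shows that the text is ambiguous. A reader might infer that the sections flatly cannot both be followed; that goes too far. But C3 does not draw the distinction, the draw count and the description of questionnaires point the other way, and no section preserves the scheduled checks after withdrawal. OMSO's described role is to review information that study staff supply, so it is no substitute once they stop supplying it.

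One could also say that the two weeks start only when the full course is finished. Neither section says so, and a volunteer withdrawn during the follow-up weeks meets the conflict on that reading too.

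Three stronger inferences are not supported:
- That the hematocrit or hemoglobin recheck due within three days is lost. B5.3 and C6.1 say that injections stop; they do not say that the volunteer is withdrawn.
- That 60 − 8 = 52 people are exposed to this gap. B5.2.2 expects 60 to be enrolled for 8 completers, but consent is signed before screening (C1.4) and screening ends once 8 have complete data. The 52 can include screen failures and people never tested; the number dosed among them could be zero.
- That all adverse-event reporting ends at withdrawal. The scheduled checks are at issue; the general reporting duties in C8 remain.

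Finally, a volunteer who leaves by choice may refuse follow-up, so the point is weaker there. The consent pages were not available and may already deal with it; the protocol sections would still need to agree.

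**Conclusion.** The concern holds as an unresolved conflict of wording. C3, applied as written, removes from a dosed and withdrawn volunteer whatever remains of a safeguard that C6.1 lists against the drug's risks. The ceiling is 2 draws and about 14 daily checks per person. It makes scheduled safety capture less complete for leavers than for finishers. Endpoints and planned efficacy analyses are not touched.

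This rests on two assumptions: that a site would apply C3 literally, and that the promised two weeks are meant for any dosed volunteer, since neither section restricts them. It is strongest for investigator withdrawal. It does not extend to volunteers whose injections are stopped on hematocrit or hemoglobin but who remain in the study. The text concerns a stated protection for healthy volunteers and is cheap to mend, so it should be corrected even though the number affected is unknown and may be small.

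**What to change.** Reconcile C3 with B5.3 and C6.1. C3, and the consent if it does not already do so, should state:
- whether data collection includes the post-EPO safety monitoring already promised; and
- whether that monitoring continues for dosed volunteers who leave early and agree to it.

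Which answer is right is a clinical and ethical decision for the sponsor and the medical office; what is needed here is that the sections give one answer. The SAP describes no adverse-event summary, so it should add that adverse events are reported for everyone who received EPO, with the length of follow-up shown for those who left early.

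Cost: a few sentences in C3, the consent and the SAP. If monitoring continues, the burden is at most the 2 draws and about 14 daily checks already planned for each early leaver. Some will decline, and the report should say how many.

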adaptations due to reduced iron efflux during overtraining to aid in the maintenance of physical performance has not been explored.

B3. MILITARY RELEVANCE

This study supports the Military Operational Medicine Research Program's Physiological Health and Performance Program Area under the BPE Work Unit. The BPE Work Unit is intent is to execute basic and applied research aimed at identifying and develop biomedical strategies and solutions that safely and ethically enhance Warfighter physical, cognitive, sensory and behavioral performance in training and operational environments, enabling lethality and overmatch. The proposed work aligns to the Physiological Health and Performance Strategic Plan Technical Challenge 1.1.1.1: Identify pharmacological enhancement protocols improving specific task performance under operational stress.

B4. OBJECTIVES/SPECIFIC AIMS/RESEARCH QUESTIONS

Objective

1. Determine the effects of EPO on hematological adaptions compared to baseline during 4 weeks of overtraining.
2. Determine the time course change in physical performance (time trial) with EPO compared to baseline.
3. Assess the influence of EPO non-hematological adaptation (whole-body and skeletal muscle substrate oxidation and glucose turnover) following 4 weeks of overtraining compared to baseline.

Hypothesis

1. Hemoglobin and hematocrit will be maintained with EPO during 4 weeks of overtraining.
2. Physical performance will be maintained with EPO during 4 weeks of overtraining.
3. EPO will increase whole body and skeletal muscle fat oxidation, and reduce reliance on endogenous glucose store following 4 weeks of physical training.

B5. RESEARCH PLAN

B5.1 Research Design

This study will be a longitudinal trial.

B5.2 Research Subjects/Population(s)

B5.2.1 Subject Population(s)

Subject population will be military or civilians representative of active duty male and female service members, being in good health and recreationally active.

B5.2.2 Number of Subjects, Records, and/or Specimens

A total of 8 volunteers will be required to achieve sufficient statistical power. To complete testing on 8 volunteers, we estimate we will need to enroll 60 individuals. All screening will stop once complete data has been collected on 8 volunteers. Records and specimen collection are described in the Research Procedures and Data Collection sections. During briefings and consenting potential participants will be informed that even though they may be eligible and want

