Study Design Overview: Healthy physically active individuals will be recruited to participate in this longitudinal trial. After baseline assessments of body composition, resting metabolic rate (RMR), $\text{VO}_{2\text{peak}}$ and exercise familiarization; volunteers will complete physical performance and substrate oxidation testing (Figure 3). Physical performance will be assessed using time trial. Substrate oxidation will be assessed by volunteers performing 90-min of steady-state load carriage (30% body mass) exercise on a treadmill at $55 \pm 5\%$ of their $\text{VO}_{2\text{peak}}$. 6-6-[$^2\text{H}_2$] glucose will be used as a tracer to assess glucose turnover. Indirect calorimetry will be used to determine carbohydrate and fat oxidation. Muscle biopsies will be performed to measure muscle glycogen, enzyme activity, and molecular markers of substrate metabolism before, immediately after, and 3-hrs post exercise. Multiple blood samples will be collected on substrate oxidation protocol days. To minimize carry over effects of muscle biopsies on subsequent exercise performance, volunteers will not exercise for 3 days. During the first two days of this period, volunteers will undergo carbon monoxide (CO) rebreathing to measure Hgb mass and blood volume. Volunteers will then receive EPO injections 3 times a week for 4 weeks. During the injection period all volunteers will have safety blood draws to assess Hct once a week. Volunteers will also complete a physical performance test once a week to determine time course change in performance with EPO compared to baseline. Exercise training will be controlled during the injection phase, consisting of a combination of endurance- and resistance-type exercise. During the final week of the injection phase body composition, resting metabolic rate (RMR) and $\text{VO}_{2\text{peak}}$ will be reassessed. At the end of the 4-week injection phase volunteers will complete a final physical performance test and substrate oxidation protocol, followed by two CO rebreathing tests on subsequent days. All food and beverages (except water) will be provided to volunteers beginning at the pre injection physical performance and substrate oxidation through the duration of the study. All data collection will occur at USARIEM.

Figure 3: Study Timeline

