5.7.1.1 FDA-approved device being used in this research according to the approved labeling

DEXA, DPX-IQ, Lunar Corporation, True Max 2400, Parvomedics, Sandy, Utah, USA, Polar Electro Inc, Oulu, Finland

5.7.1.2 FDA-approved device being used in this research in a manner other than its approved labeling: N/A

B5.7.2 Drugs

B5.7.2.1 FDA-approved and used in accordance with the approved labeling

B5.7.2.2 FDA-approved and used in a manner not in accordance with its approved labeling:
PROCRIT, EPOETIN ALFA, Janssen Products, LP, Titusville, NJ, USA

B5.7.2.3 Any drug not approved by the FDA: N/A

B5.8 Statistical Analysis

B5.8.1 Sample Size Estimation

Based on results for multiple outcomes across different studies (**Table 4**) a sample size of 8 is required to statistical significance.

Table 4: Previous study effect sizes

Study	Outcome	Delta	Effect Size	Sample Size
Thomson et al. (18)	TTE	10 ± 6	1.40	7
Plenge et al. (24)	Hct	5.1 ± 3	1.56	7
Caillaud et al. (19)	CHO Oxidation	0.7 ± 0.3	1.24	4
Caillaud et al. (19)	Fat Oxidation	0.2 ± 0.05	3.51	2

B5.8.2 Data analysis

Statistical analyses will be conducted using either SPSS (IBM Corp. Armonk, NY), SAS 9.3 (SAS Institute Inc., Carey, NC), or equivalent. Common descriptive statistics will be used to describe volunteer characteristics. Shapiro-Wilk tests will be used to determine normality of data. Paired t-tests will be used to assess phase effects (PRE vs. POST injection) for glucose turnover, and substrate oxidation. Repeated measures ANOVA will be used to assess main effects of time for physical performance. Mixed-model repeated measure ANOVA will be used to assess main effects of phase (PRE vs. POST injection), time and their interaction for blood analytes and muscle molecular analysis. If interactions are significant, appropriate post-hoc correction will be used to examine these relationships. Correlation coefficients and multiple regression analysis will be used to evaluate relationships between study outcome measures. The alpha level will be adjusted for multiple comparisons, with the level for statistical significance set at $P < 0.05$.

SECTION C: HUMAN RESEARCH PROTECTIONS

C1. RECRUITMENT AND CONSENT

C1.1 Identification and Selection of Subjects

Volunteers will be recruited from the federally and non-federally employed civilian population, the Natick Human Research Volunteer (HRV) Pool, and NSSC active duty military personnel.

C1.2 Recruitment Process

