18 March 2025

PROTOCOL TITLE: Impact of erythropoietin on hematological adaptations and physical performance

NCT: 05078138

B5.8.1 Sample Size Estimation

Based on results for multiple outcomes across different studies (**Table 1**) a sample size of 8 is required to statistical significance.

Table 1: Previous study effect sizes

Study	Outcome	Delta	Effect Size	Sample Size
Thomson et al.	TTE	10 ± 6	1.40	7
Plenge et al.	Hct	5.1 ± 3	1.56	7
Caillaud et al.	CHO Oxidation	0.7 ± 0.3	1.24	4
Caillaud et al.	Fat Oxidation	0.2 ± 0.05	3.51	2

B5.8.2 Data analysis

Statistical analyses will be conducted using either SPSS (IBM Corp. Armonk, NY), SAS 9.3 (SAS Institute Inc., Carey, NC), or equivalent. Common descriptive statistics will be used to describe volunteer characteristics. Shapiro-Wilk tests will be used to determine normality of data. Paired t-tests will be used to assess phase effects (PRE vs. POST injection) for glucose turnover, and substrate oxidation. Repeated measures ANOVA will be used to assess main effects of time for physical performance. Mixed-model repeated measure ANOVA will be used to assess main effects of phase (PRE vs. POST injection), time and their interaction for blood analytes and muscle molecular analysis. If interactions are significant, appropriate post-hoc correction will be used to examine these relationships. Correlation coefficients and multiple regression analysis will be used to evaluate relationships between study outcome measures. The alpha level will be adjusted for multiple comparisons, with the level for statistical significance set at $P < 0.05$.

References

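### Recruiting until eight volunteers are complete, with no rule for withdrawals and no control arm, leaves the performance-maintained conclusion resting in practice on completers

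*Protocol*

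**What the plan says.** - **Hypothesis (Protocol B4).** "Physical performance will be maintained with EPO during 4 weeks of overtraining". No margin is given.
- **Design (B5.1, B5.3).** One group is compared with its own baseline. Wording about groups and arms under Study Exercise and Load Carriage Exercise in B5.3 has no second arm behind it.
- **Recruitment (B5.2.2).** "All screening will stop once complete data has been collected on 8 volunteers".
- **Measurement (B5.3, Study Design Overview).** "Volunteers will also complete a physical performance test once a week to determine time course change in performance with EPO compared to baseline".
- **Withdrawal (C3).** Volunteers may leave at any time, and the investigator may stop anyone who cannot or will not carry out the procedures. "An investigator may also withdraw a volunteer if the individual becomes ill or injured". In all these cases, "all further data collection will discontinue". The same section adds: "Any samples or data collected prior to withdrawal will be maintained".
- **Analysis (SAP B5.8.2, same text in the protocol).** "Repeated measures ANOVA will be used to assess main effects of time for physical performance". For blood analytes and muscle markers the plan differs: "Mixed-model repeated measure ANOVA will be used to assess main effects of phase (PRE vs. POST injection), time" and their interaction. No analysis set, missing-data method or rule for withdrawn volunteers appears in either document.
- **Safety follow-up (B5.3 Erythropoietin Injections; C6.1 Exogenous EPO).** Monitoring is promised for two weeks after the last injection. C3 makes no exception for it.

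**The concern.** Together these rules replace incomplete volunteers until eight are complete, and analyse performance with a method that usually needs complete records. Training costs 1000-1500 kcal per day, four days a week plus a time trial. A volunteer who becomes ill, is injured or cannot continue under that load is plausibly one whose performance was falling. Leaving such people out moves the average towards the hypothesised result, and a single-group design offers nothing that would show it.

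The hypothesis makes this worse. Because the claim is maintenance with no margin, a non-significant time effect could be read as support, and completer selection makes a real decline easier to miss.

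A separate safety point comes from the same sentence. C6.1 lists clots, myocardial infarction and stroke among the EPO risks. Read literally, C3 leaves it unclear whether a volunteer withdrawn after dosing still gets the post-injection blood draws and vital signs.

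**Working it through.** **The plan's own figure.** The stated sample size is 8. Exact paired t-test calculations from the stated effect sizes (two-sided 0.05; 80% power assumed, since none is stated) need 7 for TTE (effect size 1.40), 6 for Hct (1.56), 8 for CHO oxidation (1.24) and 3 for fat oxidation (3.51). The largest is 8, so the total reproduces, although individual rows differ from the table. It makes no allowance for withdrawal; replacement does that job.

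**Inputs not in the documents.** Dosed attrition is not stated. The 60 enrolled for 8 complete is not a dropout rate, because consent precedes screening (C1.4). A range is therefore assumed. Starters behind 8 completers are 8/(1 - d), rounded up: 9 at 10%, 10 at 20%, 12 at 30%.

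**Simulation.** There were 3,000 trials per scenario (Monte Carlo SE 0.006).
- Five time trials: baseline and weeks 1-4.
- Random intercept and slope. The slope contributes SD 0.9 to the week-4 change and the residual SD is 0.31, so the variance of that change is 0.9² + 2 × 0.31² = 0.81 + 0.19 = 1.00.
- Weekly withdrawal is logistic in the decline, with slope 0.5, 1 or 2 per SD.
- Recruitment continues until 8 are complete.

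Bias in the week-4 change (SD units; positive is favourable) when the true change is zero:

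| Withdrawal | Depends on | Logistic slope | Completers | Mixed model, all dosed |
|---|---|---|---|---|
| 20% | last observed change | 0.5 / 1 / 2 | 0.040 / 0.086 / 0.154 | 0.003 / 0.016 / 0.015 |
| 20% | unobserved next change | 0.5 / 1 / 2 | 0.074 / 0.129 / 0.229 | 0.034 / 0.054 / 0.103 |
| 10% | last observed / next | 1 | 0.042 / 0.073 | 0.007 / 0.037 |
| 30% | last observed / next | 1 | 0.119 / 0.189 | 0.002 / 0.080 |

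At 20% withdrawal, RMSE is 0.35-0.39 for completers and 0.33-0.35 for the mixed model. The standard error with eight volunteers is 1/√8 = 0.35 SD. A repeat run at 20% and slope 1 gave completer bias of 0.09-0.16 SD and mixed-model bias of 0.03-0.09 SD, so the mixed-model figures above may be somewhat optimistic.

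**Missing a real decline.** Take a true fall of 1 SD and a two-sided 0.05 test of week 4 against baseline on 7 df. With eight volunteers and no withdrawal, the noncentrality is 1 × √8 = 2.83 and the test misses 31.9% of the time. With 20% withdrawal, completers miss it in 35.3-45.0% of trials. The mixed model, with about 10 dosed, misses it in 27.1-29.5%.

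**A second selection model.** Suppose the least tolerant fraction d withdraws and tolerance correlates ρ with the performance change. The completers' mean then shifts by ρ·φ(z_d)/(1 - d). At d = 0.20, φ(z_d)/(1 - d) = 0.35, giving 0.35 × 0.5 = 0.18 to 0.35 × 0.7 = 0.25 SD. The direction is the same and the shift somewhat larger.

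**Less favourable variances.** With a slope SD of 0.5 and a residual SD of 0.61 (week-4 change SD still about 1), logistic slope 1 and no true change:
- Withdrawal on the unobserved next value: bias falls only from 0.13 to 0.08 SD, and RMSE from 0.36 to 0.34.
- Withdrawal on observed values: the two methods are about equal in size of bias (+0.04 for completers, -0.03 SD for the mixed model).
- Mixed-model convergence falls from over 99% to 93-95%.
- A true 1 SD decline, with withdrawal on the next value, is missed in 43% of trials with completers and 38% with the mixed model.

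**The case against.** The strongest reply is that no document declares a completers-only analysis. The complete-data sentence is a rule for stopping screening, C3 keeps data collected before withdrawal, and the software named could fit a model that uses partial records. That is true, and it is why the concern says in practice. But no rule says the partial trials will be used, the planned method in its usual form excludes them, and a withdrawn volunteer has no week-4 trial.

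Direction and size are also assumed. With six biopsies, 26 blood draws and only study food, some volunteers will leave for reasons unrelated to running performance; such withdrawals add no bias. Stopping EPO for high Hct or rising hemoglobin is not called withdrawal, so those volunteers may stay in. Both points limit the size without removing the risk.

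The bias is below one standard error, and the gain from the mixed model shrinks under less favourable variances. The main simulation fits the model that generated its data and makes earlier weeks strongly predictive. These points stand and keep the concern moderate.

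Much of the missed-decline figure comes from having eight volunteers. Selection adds about 3 to 13 percentage points to the 32% baseline, and part of the mixed model's advantage is simply that it uses about 10 volunteers. That also stands.

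A control arm would not by itself remove completer selection. It would supply a comparator under the same load and reveal differential dropout.

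Finally, the medical support office is responsible for adverse events, and the monitoring promise is not limited to completers. C3 is therefore ambiguous on safety follow-up, and one sentence settles it.

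**Conclusion.** The concern holds. The recruitment, withdrawal and analysis rules together make the week-4 performance conclusion rest in practice on volunteers who completed overtraining, and the likely direction of error favours the hypothesis. At an assumed 20% withdrawal the favourable bias is 0.04-0.23 SD; at 10% and 30% (logistic slope 1) it is 0.04-0.07 and 0.12-0.19 SD. These figures rest on assumed attrition, variances and withdrawal mechanisms, none of which the documents give. Confidence in the structure is good and in the size only medium. This should be changed because the remedy is cheap and the data needed are already retained; it does not invalidate the study. If nobody withdraws after dosing, the selection effect disappears.

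**What to change.** **In B5.8.2 (protocol and SAP):**
- Analyse the weekly time trials, and the weekly Hgb and Hct, with a linear mixed model (REML, small-sample degrees of freedom). Include all volunteers with a baseline and at least one EPO injection, and use all data up to withdrawal.
- Show the eight completers as a sensitivity analysis.
- Report how many were dosed, stopped and replaced, with reasons. C3 already asks that reasons for withdrawal be documented.
- State the limits: the model removes bias only as far as earlier observed values predict withdrawal, and it cannot recover outcomes measured only PRE and POST (glucose turnover, substrate oxidation).

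**In C3:** add that any volunteer withdrawn after at least one EPO dose will be offered, with their agreement, the two-week post-injection monitoring described in B5.3 and C6.1.

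**Cost:** SAP wording and one sentence in C3. No extra recruitment is needed, and a mixed-model analysis is already planned for blood analytes. The price is slightly more modelling work, unbalanced data, possible convergence problems at this size (a simpler covariance structure should be named in advance as a fallback), and up to two follow-up visits per withdrawn volunteer who agrees.
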